### 9.2.4 Storage

Store intact vials of ipilimumab refrigerated at 2-8 °C (36-46°F). Protect from light. DO NOT FREEZE OR SHAKE. The formulation contains no preservatives.

If a storage temperature excursion is identified, promptly return ipilimumab to 2°C-8°C and quarantine the supplies. Provide a detailed report of the excursion (including documentation of temperature monitoring and duration of the excursion) to [[contact]](mailto:[contact]) for determination of suitability.

### 9.2.5 Solution Preparation

Ipilimumab may be dispensed undiluted or further diluted in 0.9% NaCl Injection, USP or 5% Dextrose Injection, USP to a concentration between 1 mg/mL and 4 mg/mL. Ipilimumab is stable in polyvinyl chloride (PVC), non-PVC/non DEHP (di-(2-ethylhexyl) phthalate) IV bag or glass container. Ipilimumab diluted between 1 mg/mL and 4 mg/mL is stable in polypropylene syringes. Mix GENTLY by inverting several times. **Do not shake.** Vials of ipilimumab for injection do not contain preservatives; the product should be prepared as soon as possible prior to administration using aseptic technique.

### 9.2.6 Stability

Shelf-life surveillance of the intact vials is ongoing. Prepared solutions of ipilimumab undiluted (5 mg/mL) or diluted with 0.9% sodium chloride are stable for up to 24 hours refrigerated (2 – 8° C) or at room temperature (under room light).

### 9.2.7 Administration

See Treatment and Dose Modifications sections of the protocol.

Ipilimumab is administered as a 90-minute intravenous infusion using a volumetric pump and a PVC IV infusion set with an in-line, sterile, non-pyrogenic, low-protein-binding filter (0.2 micron to 1.2 micron). Do NOT administer as an intravenous push or bolus. **For administration by syringe pump, the concentration of Ipilimumab must be within the range of 1 mg/mL and 4 mg/mL.**

When administered in combination with nivolumab, infuse nivolumab first followed by ipilimumab on the same day. Use separate infusion set and filters for each infusion.

### 9.2.8 Ipilimumab Toxicities

The Comprehensive Adverse Events and Potential Risks list (CAEPR) provides a single list of reported and/or potential adverse events (AE) associated with an agent using a uniform presentation of events by body system. In addition to the comprehensive list, a subset, the Specific Protocol Exceptions to Expedited Reporting (SPEER), appears in a separate column and is identified with bold and italicized text. This subset of AEs (SPEER) is a list of events that are protocol specific exceptions to expedited reporting to NCI (except as noted below). Refer to the 'CTEP, NCI Guidelines: Adverse Event Reporting Requirements' [http://ctep.cancer.gov/protocolDevelopment/electronic\\_applications/docs/aeguidelines.pdf](http://ctep.cancer.gov/protocolDevelopment/electronic_applications/docs/aeguidelines.pdf) for further clarification. *Frequency is provided based on 2678 patients.* Below is the CAEPR for Ipilimumab (MDX-010).

**NOTE:** Report AEs on the SPEER **ONLY IF** they exceed the grade noted in parentheses next to the AE in the SPEER. If this CAEPR is part of a combination protocol using multiple investigational agents and has an AE listed on different SPEERs, use the lower of the grades to determine if expedited reporting is required.

**Version 2.10, March 29, 2019**

Adverse Events with Possible Relationship to Ipilimumab (MDX-010) (CTCAE 5.0 Term) [n= 2678]			Specific Protocol Exceptions to Expedited Reporting (SPEER)
Likely (>20%)	Less Likely (<=20%)	Rare but Serious (<3%)	
BLOOD AND LYMPHATIC SYSTEM DISORDERS			
		Blood and lymphatic system disorders - Other (acquired hemophilia)	
CARDIAC DISORDERS			
	Atrial fibrillation		
		Myocarditis 	
		Pericardial effusion	
EAR AND LABYRINTH DISORDERS			
	Hearing impaired		
ENDOCRINE DISORDERS			
	Adrenal insufficiency 		
	Hyperthyroidism 		
	Hypophysitis 		
	Hypopituitarism 		
	Hypothyroidism 		
	Testosterone deficiency 		
EYE DISORDERS			
	Eye disorders - Other (episcleritis) 		
	Uveitis 		
GASTROINTESTINAL DISORDERS			
	Abdominal pain		
	Colitis 		Colitis (Gr 3)
		Colonic perforation 	
	Constipation		
Diarrhea			Diarrhea (Gr 3)
	Enterocolitis		
	Esophagitis		
		Ileus	
Nausea			Nausea (Gr 3)
	Pancreatitis 		
	Vomiting		
GENERAL DISORDERS AND ADMINISTRATION SITE CONDITIONS			
	Chills		
Fatigue			Fatigue (Gr 3)
	Fever		Fever (Gr 2)
		General disorders and administration site conditions - Other (Systemic inflammatory response syndrome [SIRS])	
		Multi-organ failure	
HEPATOBIILIARY DISORDERS			
	Hepatobiliary disorders - Other (hepatitis) 		
IMMUNE SYSTEM DISORDERS			
	Autoimmune disorder 		
		Immune system disorders - Other (GVHD in the setting of allotransplant) 	

Adverse Events with Possible Relationship to Ipilimumab (MDX-010) (CTCAE 5.0 Term) [n= 2678]			Specific Protocol Exceptions to Expedited Reporting (SPEER)
Likely (>20%)	Less Likely (<=20%)	Rare but Serious (<3%)	
INFECTIONS AND INFESTATIONS			
		Infections and infestations - Other (aseptic meningitis) 	
INJURY, POISONING AND PROCEDURAL COMPLICATIONS			
	Infusion related reaction		
INVESTIGATIONS			
	Alanine aminotransferase increased		
	Aspartate aminotransferase increased		
		Lymphocyte count decreased	
	Neutrophil count decreased		
	Weight loss		
METABOLISM AND NUTRITION DISORDERS			
	Anorexia		
	Dehydration		
	Hyperglycemia		
		Metabolism and nutrition disorders - Other (exacerbation of pre-existing diabetes mellitus)	
MUSCULOSKELETAL AND CONNECTIVE TISSUE DISORDERS			
	Arthralgia		
	Arthritis		
		Generalized muscle weakness	
	Musculoskeletal and connective tissue disorder - Other (polymyositis) 		
NERVOUS SYSTEM DISORDERS			
		Ataxia	
	Facial nerve disorder 		
	Guillain-Barre syndrome 		
	Headache		
	Myasthenia gravis 		
		Nervous system disorders - Other (immune-mediated encephalitis) 	
		Peripheral motor neuropathy	
		Peripheral sensory neuropathy	
	Trigeminal nerve disorder		
PSYCHIATRIC DISORDERS			
		Psychiatric disorders - Other (mental status changes)	
RENAL AND URINARY DISORDERS			
	Acute kidney injury		
	Renal and urinary disorders - Other (granulomatous tubulointerstitial nephritis)		
RESPIRATORY, THORACIC AND MEDIASTINAL DISORDERS			
	Pneumonitis		
		Respiratory failure	

Adverse Events with Possible Relationship to Ipilimumab (MDX-010) (CTCAE 5.0 Term) [n= 2678]			Specific Protocol Exceptions to Expedited Reporting (SPEER)
Likely (>20%)	Less Likely (<=20%)	Rare but Serious (<3%)	
		Respiratory, thoracic and mediastinal disorders - Other (bronchiolitis obliterans with organizing pneumonia)	
		Respiratory, thoracic and mediastinal disorders - Other (lung infiltration)	
SKIN AND SUBCUTANEOUS TISSUE DISORDERS			
		Erythema multiforme	
	Pruritus		Pruritus (Gr 3)
Rash maculo-papular			Rash maculo-papular (Gr 3)
	Skin and subcutaneous tissue disorders - Other (Sweet's Syndrome)		
		Stevens-Johnson syndrome	
		Toxic epidermal necrolysis	
	Urticaria		
VASCULAR DISORDERS			
	Hypotension		

This table will be updated as the toxicity profile of the agent is revised. Updates will be distributed to all Principal Investigators at the time of revision. The current version can be obtained by contacting [[contact]](mailto:[contact]). Your name, the name of the investigator, the protocol and the agent should be included in the e-mail.

Ipilimumab can result in severe and fatal immune-mediated adverse events probably due to T-cell activation and proliferation. These can include (but are not limited to) autoimmune hemolytic anemia, acquired anti-factor VIII immune response, autoimmune aseptic meningitis, autoimmune hepatitis, autoimmune thyroiditis, hepatic failure, pure red cell aplasia, pancreatitis, ulcerative and hemorrhagic colitis, endocrine disorders (e.g., autoimmune thyroiditis, hyperthyroidism, hypothyroidism, autoimmune hypophysitis/hypopituitarism, and adrenal insufficiency), ocular manifestations (e.g., uveitis, iritis, conjunctivitis, blepharitis, and episcleritis), sarcoid granuloma, myasthenia gravis, polymyositis, and Guillain-Barre syndrome. The majority of these reactions manifested early during treatment; however, a minority occurred weeks to months after discontinuation of ipilimumab especially with the initiation of additional treatments.

Late bowel perforations have been noted in patients receiving MDX-010 (ipilimumab) in association with subsequent IL-2 therapy.

Complications including hyperacute graft-versus-host disease (GVHD), may occur in patients receiving allo stem cell transplant (SCT) after receiving Ipilimumab (MDX-010). These complications may occur despite intervening therapy between receiving Ipilimumab (MDX-010) and allo-SCT.

In rare cases diplopia (double vision) has occurred as a result of muscle weakness (Myasthenia gravis).

Gastrointestinal hemorrhage includes Anal hemorrhage, Cecal hemorrhage, Colonic hemorrhage, Duodenal hemorrhage, Esophageal hemorrhage, Esophageal varices hemorrhage, Gastric hemorrhage, Hemorrhoidal hemorrhage, Ileal hemorrhage, Intra-abdominal hemorrhage, Jejunal hemorrhage, Lower gastrointestinal hemorrhage, Oral hemorrhage, Pancreatic hemorrhage, Rectal hemorrhage, Retroperitoneal hemorrhage, and Upper gastrointestinal hemorrhage under the GASTROINTESTINAL

## DISORDERS SOC.

Infection includes all 75 sites of infection under the INFECTIONS AND INFESTATIONS SOC.

**Adverse events reported on Ipilimumab (MDX-010) trials, but for which there is insufficient evidence to suggest that there was a reasonable possibility that Ipilimumab (MDX-010) caused the adverse event:**

**BLOOD AND LYMPHATIC SYSTEM DISORDERS** - Anemia; Blood and lymphatic system disorders - Other (pure red cell aplasia); Febrile neutropenia  
**CARDIAC DISORDERS** - Conduction disorder; Restrictive cardiomyopathy  
**EYE DISORDERS** - Extraocular muscle paresis; Eye disorders - Other (retinal pigment changes)  
**GASTROINTESTINAL DISORDERS** - Colonic ulcer; Dyspepsia; Dysphagia; Gastrointestinal disorders - Other (gastroenteritis); Gastrointestinal hemorrhage; Proctitis  
**GENERAL DISORDERS AND ADMINISTRATION SITE CONDITIONS** - Flu like symptoms; Non-cardiac chest pain  
**HEPATOBIILIARY DISORDERS** - Hepatic failure  
**IMMUNE SYSTEM DISORDERS** - Allergic reaction  
**INFECTIONS AND INFESTATIONS** - Infection  
**INVESTIGATIONS** - Creatinine increased; Investigations - Other (rheumatoid factor); Lipase increased; Platelet count decreased; Serum amylase increased; White blood cell decreased  
**METABOLISM AND NUTRITION DISORDERS** - Tumor lysis syndrome  
**MUSCULOSKELETAL AND CONNECTIVE TISSUE DISORDERS** - Back pain; Joint range of motion decreased; Myalgia; Pain in extremity  
**NEOPLASMS BENIGN, MALIGNANT AND UNSPECIFIED (INCL CYSTS AND POLYPS)** - Tumor pain  
**NERVOUS SYSTEM DISORDERS** - Dizziness; Dysphasia; Ischemia cerebrovascular; Seizure  
**PSYCHIATRIC DISORDERS** - Anxiety; Confusion; Depression; Insomnia  
**RENAL AND URINARY DISORDERS** - Proteinuria  
**RESPIRATORY, THORACIC AND MEDIASTINAL DISORDERS** - Allergic rhinitis; Cough; Dyspnea; Laryngospasm  
**SKIN AND SUBCUTANEOUS TISSUE DISORDERS** - Alopecia; Dry skin; Hyperhidrosis; Skin hypopigmentation  
**VASCULAR DISORDERS** - Flushing; Hypertension; Vascular disorders - Other (temporal arteritis)

**Note:** Ipilimumab (BMS-734016; MDX-010 Transfectoma-derived) in combination with other agents could cause an exacerbation of any adverse event currently known to be caused by the other agent, or the combination may result in events never previously associated with either agent.

#### 9.2.9 Agent Ordering and Agent Accountability

NCI supplied agents may be requested by the eligible participating investigator (or their authorized designee) at each participating institution. Pharmaceutical Management Branch (PMB) policy requires that agent be shipped directly to the institution where the patient is to be treated. PMB does not permit the transfer of agents between institutions (unless prior approval from PMB is obtained.) The CTEP assigned protocol number must be used for ordering all CTEP supplied investigational agents. The responsible investigator at each participating institution must be registered with CTEP, DCTD through an annual submission of FDA form 1572 (Statement of Investigator), NCI Biosketch, Agent Shipment Form, and Financial Disclosure Form (FDF). If there are several participating investigators at one institution, CTEP supplied investigational agents for the study should be ordered under the name of one lead participating investigator at that institution.

#### 9.2.10 Clinical Drug Request and Investigator Brochure Availability

Submit agent requests through the PMB Online Agent Order Processing (OAOP) application. Access to OAOP requires the establishment of a CTEP Identity and Access Management (IAM) account and the maintenance of an “active” account status, a “current” password, and active person registration status. For questions about drug orders, transfers, returns, or accountability call or email PMB anytime. Refer to the PMB’s website for specific policies and guidelines related to agent management. Questions about IB access may be directed to the PMB IB coordinator via email.

The current versions of the IBs for the agents will also be accessible to site investigators and research staff through the PMB Online Agent Order Processing (OAOP) application. Questions about IB access may be directed to the PMB IB coordinator via email.

#### 9.2.11 Agent Inventory Records

The investigator, or a responsible party designated by the investigator, must maintain a careful record of the inventory and disposition of all agents received from the PMB using the appropriate NCI Investigational Agent (Drug) Accountability Record (DARF) available on the CTEP forms page. Store and maintain separate NCI Investigational Agent Accountability Records for each agent, strength, formulation and ordering investigator on this protocol.

## 10.0 **CRITERIA FOR REMOVAL FROM PROTOCOL THERAPY AND OFF STUDY CRITERIA**

### 10.1 **Criteria for Removal from Protocol Therapy**

- a) Clinical (including physical examination or serum tumor markers) or radiographic evidence of progressive disease of greater than 40% increase from baseline target lesions selected according to RECIST criteria (See [Section 12.0](#)).
- b) Clinical (including physical examination or serum tumor markers) or radiographic evidence of progressive disease > 12 weeks after start of protocol therapy.
- c) Adverse Events requiring removal from protocol therapy (See [Sections 5.4](#) and [6.0](#)).
- d) Immune adverse events requiring removal from protocol therapy (See [Section 5.4](#)

- and [Section 6.0](#)) which in the opinion of the treating physician are consistent with acute or chronic GVHD requiring systemic immunosuppression.
- e) Refusal of further protocol therapy by patient/parent/guardian
  - f) Non-compliance that in the opinion of the investigator does not allow for ongoing participation.
  - g) Physician determines it is not in the patient's best interest.
  - h) Repeated eligibility laboratory studies (CBC with differential, bilirubin, ALT (SGPT) or serum creatinine) are outside the parameters required for eligibility prior to the start of protocol therapy (See [Section 8.1](#)).
  - i) Study is terminated by Sponsor.
  - j) Pregnancy

**Patients who are removed from protocol therapy during cycle 1 (Part A and B) or during cycles 1 and 2 (Parts C, D, or E) should continue to have the required observations in [Section 8.1](#) until the originally planned end of the cycle or until all adverse events have resolved per [Section 13.4.4](#), whichever happens LATER. The only exception is with documentation of the patient's withdrawal of consent. Patients who are removed from protocol therapy in subsequent cycles should have the necessary observations to ensure adequate clinical care.**

Patients who are off protocol therapy are to be followed as described in [Section 8.1.1](#) until they meet the criteria for Off Study (see below). Ongoing adverse events, or adverse events that emerge after the patient is removed from protocol therapy, but within 100 days of the last dose of investigational agent, must be followed and reported via RAVE and CTEP-AERS (if applicable). Serious adverse events that occur during the follow-up period (more than 30 days after the last administration of investigational agent) and have an attribution of possible, probable, or definite require reporting per [Footnote 1](#) of Table A. Follow-up data will be required unless consent is withdrawn.

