Except for patients with neuroblastoma and MIBG only disease, response assessment will use standard RECIST criteria. Determination of progression will use target selection and single dimension measurements according to RECIST criteria. Patients will be removed from study if tumor size increases from baseline in target lesions selected according to RECIST criteria. However, because a minority of subjects treated with immunotherapy may derive clinical benefit despite initial evidence of progressive disease (e.g. pseudoprogression) patients will be allowed to remain on study if the magnitude of increase in tumor size is <40% and the bulleted criteria below are met. Patients who develop a new lesion while on study are eligible to remain on study if they meet the criteria bulleted below and the sum of the total tumor burden remains < 40% according to RECIST criteria. These are adapted from similar criteria already in place in trials of checkpoint inhibitors in adults with cancer and have been utilized in the Phase I trial of ipilimumab in children. Additional criteria required in order to allow a patient to remain on study despite an increase in tumor size of > 20% but < 40% are the following:

- In the judgment of the treating clinician, the patient does not show evidence for rapid disease progression and/or the patient has shown evidence for clinical benefit.

- There is no decrease in performance status.
- The patient is tolerating the study drug and has not experienced a DLT.
- Continued treatment with nivolumab alone or in combination with ipilimumab will not delay an imminent intervention required to prevent a serious complications (e.g. CNS metastases which require radiation therapy or surgery).

For patients who remain on study despite increase in tumor size of > 20%, imaging to include target lesions must occur following every cycle if clinically indicated, and the same radiographic and clinical criteria must be met in order to remain on study. If tumor size subsequently diminishes to < 20% increase from baseline, the patient may be followed according to the standard protocol guidelines which will involve less frequent imaging. The decision to continue treatment beyond radiographic evidence for disease progression should be discussed with the Study Chair and/or her designee and documented in the study record.

Response for patients with MIBG only neuroblastoma will be assessed according to [Section 12.4.2](#).

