### Exceptions for Delayed Response (‘pseudoprogression’)

Patients in whom the magnitude of increase in tumor size is >20% but <40%, may remain on study for up to 12 weeks after start of protocol therapy if the following criteria are met. Lesions < 10 mm will not be considered new lesions; new lesions  $\geq$  10 mm of longest diameter must be included in the total tumor burden.

- In the judgment of the treating clinician, the patient does not show evidence for rapid disease progression or the patient has shown evidence for clinical benefit.
- There is no decrease in performance status.
- The patient is tolerating the study drug and there has been no DLT.
- Continued treatment with nivolumab alone or in combination with ipilimumab will not delay an imminent intervention required to prevent a serious complications (e.g. CNS metastases which require radiation therapy or surgery).

For patients who remain on study despite increase in tumor size > 20%, imaging to include target lesions must occur every cycle if clinically indicated, or if “pseudoprogression” appears based on inflammatory response, or sarcoid granuloma is present, and the same radiographic and clinical criteria must be met in order to remain on study. If tumor size subsequently diminishes to < 20% increase from baseline, the patient may be followed according to the standard protocol guidelines which will involve less frequent imaging. The decision to continue treatment beyond radiographic evidence for disease progression should be discussed with the study PI, and if needed, the sponsor, and documented in the study record.

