### Response Criteria for Patients with Solid Tumor and Measurable Disease

#### 12.2.5.1 Evaluation of Target Lesions

Complete Response (CR): Disappearance of all target and non-target lesions. Any pathological lymph nodes (whether target or non-target) must have reduction in short axis to <10 mm. If immunocytology is available, no disease must be detected by that methodology. Normalization of urinary catecholamines or other tumor markers if elevated at study enrollment (for patients with neuroblastoma).

Partial Response (PR): At least a 30% decrease in the sum of the diameters of target lesions, taking as reference the baseline sum diameters

Progressive Disease (PD): At least a 20% increase in the sum of the diameters of target lesions, taking as reference the smallest sum on study (this includes the baseline sum if that is the smallest on study). In addition to the relative increase of 20%, the sum must also demonstrate an absolute increase of at least 5 mm. (Note: the appearance of one or more new lesions is also considered progression. See [Section 12.2.1](#) for exception). Note: in presence of SD or PR in target disease but unequivocal progression in non-target or non-measurable disease, the patient has PD if there is an overall level of substantial worsening in non-target disease such that the overall tumor burden has increased sufficiently to merit discontinuation of therapy.

Stable Disease (SD): Neither sufficient shrinkage to qualify for PR nor

sufficient increase to qualify for PD, taking as reference the smallest sum diameters while on study

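### Section 10.1(a) leaves new lesions out of its 40% removal threshold, so before week 12 a patient whom Sections 2.5 and 12.2.1 do not let continue may meet no listed progression criterion

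*Combined protocol and SAP*

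**What the plan says.** Section 5.1.5 gives Part E treatment until a Section 10.1 criterion is met, and the sentence run into the title of Section 5.2 says the same. Section 5.2 allows the next cycle if no 10.1 item is met, the eligibility limits of Section 4.0 are met again, and there has been no DLT.

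Section 10.1 has two progression items:

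- Item (a), with no time limit: clinical or "radiographic evidence of progressive disease of greater than 40% increase from baseline target lesions selected according to RECIST criteria", followed by a pointer to Section 12.0.
- Item (b): any progressive disease, but only later than 12 weeks after the start.

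Item (g) leaves removal to the physician's judgement.

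Section 2.5 starts from the opposite default: "Patients will be removed from study if tumor size increases from baseline in target lesions selected according to RECIST criteria". By exception, "patients will be allowed to remain on study if the magnitude of increase in tumor size is <40% and the bulleted criteria below are met". A patient with a new lesion may stay only if those conditions hold and "the sum of the total tumor burden remains < 40% according to RECIST criteria".

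The delayed-response exception in Section 12.2 is printed without a number but is cited elsewhere as 12.2.1. It says that patients with growth above 20% and below 40% "may remain on study for up to 12 weeks after start of protocol therapy if the following criteria are met". New lesions of at least 10 "mm of longest diameter must be included in the total tumor burden". One of the conditions is "There is no decrease in performance status". Section 12.2.5.1 adds that "the appearance of one or more new lesions is also considered progression", subject to the same exception.

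**The concern.** The removal list is the part of the protocol that a site works through when deciding whether to give the next dose. Item (a) states its own number and its own denominator, and both differ from the rule in 2.5 and 12.2.1. It omits new lesions, and it omits the conditions that a patient must meet to stay.

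Two sites could therefore act differently on the same scan. The site that follows 10.1 item by item could keep a progressing patient on ipilimumab 3 mg/kg plus nivolumab 1 mg/kg when the other sections say that the patient may not continue.

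**Working it through.** The plan attaches no figure to this rule, so there is none to reproduce. The check compares the two rules case by case and then dates the Part E scans.

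**1. The two rules up to week 12.** Assume a baseline target sum of 100 mm, so that millimetres equal per cent. A patient with progression may stay under 2.5 and 12.2.1 if (targets + new lesions of 10 mm or more − baseline) / baseline is below 40% and all conditions hold. Item 10.1(a) is met if (targets − baseline) / baseline is above 40%.

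| Target growth | New lesions | Conditions | Total growth | May stay (2.5, 12.2.1) | 10.1(a) met |
|---|---|---|---|---|---|
| +30% | none | met | +30% | yes | no |
| +45% | none | met | +45% | no | yes |
| +25% | 20 mm | met | +45% | **no** | **no** |
| 0% | 45 mm | met | +45% | **no** | **no** |
| +30% | none | one failed | +30% | **no** | **no** (see step 3) |
| +40% | none | met | +40% | **no** | **no** |

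The first two rows agree and the others do not. The last row is only a boundary slip: one rule says below 40% and the other says above 40%.

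**2. The clear gap: new lesions.** Take targets of 60 mm growing to 66 mm, plus one new 20 mm lesion.

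- By 10.1(a): (66 − 60) / 60 = +10%.
- By 2.5 and 12.2.1: (66 + 20 − 60) / 60 = 26 / 60 = +43%.

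At +10% target growth, the new-lesion diameter that brings the total to 40% is (0.40 − 0.10) × S for a baseline sum S (assumed):

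- S = 50 mm: 15 mm
- S = 60 mm: 18 mm
- S = 100 mm: 30 mm
- S = 25 mm: 7.5 mm, so any lesion that reaches the 10 mm counting limit is enough

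**3. The smaller gap: a failed condition.** A DLT is caught by 10.1(c) and 5.2. Two of the other three conditions are clinical judgements on which the physician can act under 10.1(g). What remains is mainly a fall in performance status. Section 5.2 stops the next cycle only if the patient drops below the floor in 4.1.5, which is Karnofsky 50 (over 16 years) or Lansky 60 (16 or under). The largest falls that 5.2 does not catch are 100 − 50 = 50 Karnofsky points and 100 − 60 = 40 Lansky points. Example, age over 16: targets 50 to 65 mm, (65 − 50) / 50 = +30%, and Karnofsky 90 to 60. This patient fails 12.2.1 but still meets 4.1.5.

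**4. Timing in Part E.** Count the first dose as day 0 and assume no delays. With 21-day cycles, cycle 3 starts on day 42, cycle 4 on day 63 and cycle 5 on day 84, which is exactly 12 weeks. Table 8.1 schedules scans at the end of cycles 2 and 4 and allows studies within 72 hours before the next cycle. The scans therefore fall on days 39-42 and 81-84. Item 10.1(b) needs more than 84 days, so it applies at neither.

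**5. Doses at stake after the first scan.** Cycles 3 and 4 remain, so 2 of 4 combination doses: ipilimumab 2 × 3 = 6 of 12 mg/kg, and nivolumab 2 × 1 = 2 of 4 mg/kg.

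**The case against.** The best defence is that the intended rule is already in the protocol and several routes lead to it. Item 10.1(a) points to Section 12.0, which contains the exception. Footnote 5 of Table 8.1 repeats that the criteria must hold for a patient to stay. The schema note stops therapy for progression. Continuing past radiographic progression should be discussed with the study chair and documented, and Section 14.5 provides a weekly review. Section 5.2 permits a further cycle but does not compel it, and 10.1(g) always allows removal.

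All of this lowers the chance that a patient is wrongly kept on treatment, and it rules out one inference a reader might draw: that the protocol has no limit on treating through progression before week 12. It does have one, in 2.5 and 12.2.1. But none of these routes removes the contradictory threshold. The pointer leads to a section that disagrees with the number printed beside it. The schema note has no pseudoprogression exception, so it adds a third version. Item (g) is discretionary where 2.5 and 12.2.1 are not.

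The defence is stronger on the performance-status gap. Item (a) opens with clinical evidence. If the 40% figure is read as qualifying radiographic evidence only, a site could remove such a patient as a clinical progression. The two gaps therefore do not have equal standing. That reading does not help with new lesions, where the evidence is radiographic.

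The window is also narrow. By the second scan all four combination doses have been given, and 10.1(b) begins to apply just after it.

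**Conclusion.** The conflict stands and should be corrected in the next amendment. The firm part is the new-lesion case: total burden at 40% or more, target growth not above 40%, before 10.1(b) applies. The performance-status case is secondary and depends on how (a) is read. The exactly-40% case is trivial.

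Sections 5.1.1 to 5.1.4 mark Parts A to D as completed, so newly enrolled patients are in Part E. Section 11.7.1 caps Part E at 23, and that is a ceiling, because Part E may close after stage 1. The doses at stake are at most 2 of 4 combination doses after the first scan. This assumes no dose delays, and the lesion sizes in the examples are assumed.

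A reader might infer that a material share of Part E patients would be over-treated. The documents give no frequency for either gap, so they do not support that. A reader might also infer damage to the response endpoint or to the error rate and power of the two-stage design. Item 10.1(a) enters neither the responder definition in 11.7.2 nor the stage rule in 11.7.1, and the stated 0.07 and 0.88 are unchanged. This is a fault in a stopping list that bears on patient exposure and consistency between sites.

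**What to change.** Keep the opening of 10.1(a), clinical or radiographic progression, and its pointer to Section 12.0. Replace the 40% clause with: *unless the pseudoprogression exception in Sections 2.5 and 12.2.1 applies, that is, the sum of target lesions plus new lesions of 10 mm or more is less than 40% above baseline, every listed clinical condition is met, and no more than 12 weeks have passed since protocol therapy began*.

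- Cite 2.5 as well as 12.2.1. Section 12.2.1 is written for growth above 20% and leaves unclear a new lesion with total growth below that.
- Keeping the Section 12.0 pointer means that progression under 12.3 to 12.5 stays covered.
- Leave 10.1(b) as it is.
- Add to the schema note: *except per Section 12.2.1*.
- Adding the 12-week limit to 2.5 is optional tidying.

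The cost is one reworded line and one short addition. It needs no extra visits, scans or patients, and no change to the design.
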